9.4.2.2.3 Secondary - Immunogenicity

The percentage of responders and participants having 2FR, 4FR will be provided against each endpoint with the corresponding 95% CIs using the Clopper-Pearson method. FR is defined as fold-rise from post-vaccination relative to pre-vaccination. Differences of percentages of responders and participants with 2FR and 4FR will be provided with 95% CI calculated by the Newcombe-Wilson score method without continuity correction. GMTs or GMCs in each injection group and GMT ratios between injection groups will be summarized along with their 95% CIs using the normal approximation of log-transformed titers. GMTs will be presented in original

scale that are re-converted from log-transformed titers. GMTRs are defined as the ratio of individual geometric mean titer for each injection group. GMTR will be summarized with 95% CI (normal approximation). Additional parameters may be displayed as appropriate.

The same method will be applied for calculating the two-sided CI as in [Section 9.4.2.2.1](#).

The PPAS will be utilized for secondary immunogenicity objectives. Subgroup analyses will be performed but not limited to age group (18-55 years old and \geq 56 years old) for Intervention Groups. The secondary immunogenicity endpoints will also be evaluated on the FAS.

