	
COVID-19 vaccine will be stratified based on the vaccine received 4 to \leq 10 months prior and by age group (18-55 years of age and 56 years of age and older) and randomly assigned to 1 of the following booster formulations in a 1:1 ratio:
 
 CoV2 preS dTM-AS03 (B.1.351) CoV2 preS dTM-AS03 (D614 + B.1.351) 
Participants previously vaccinated with CoV2 preS dTM-AS03 (D614) as a primary series in the Original Phase II Cohort will be stratified by age group (18-55 years of age and 56 years of age and older) and randomly assigned to 1 of the following booster formulations in a 9:1 ratio for younger adults (D614:B.1.351) and a 1:1 ratio for older adults:
 
 CoV2 preS dTM-AS03 (D614) CoV2 preS dTM-AS03 (B.1.351) 
• Supplemental Cohort 2 Exploratory B.1.351 Arms: Participants previously vaccinated with the Pfizer/BioNTech mRNA vaccine will be enrolled after completion of enrollment of the above booster arms in Cohort 2 and will be stratified by age group (18-55 years of age and 56 years of age and older) and randomly assigned to receive 1 of the following CoV2 preS dTM (B.1.351) formulations in a 1:1:1:1 ratio:
 2.5 μg antigen with AS03 adjuvant 2.5 μg antigen with half-dose^a AS03 adjuvant 5 μg antigen with half-dose AS03 adjuvant 5 μg antigen with no adjuvant• Supplemental Cohorts Comparator Group: SARS-CoV-2-naïve, unvaccinated, adults who are 18-55 years of age will be given CoV2 preS dTM-AS03 (D614) as a primary series vaccination of 2 injections given 21 days apart.• Supplemental Cohort Subsets and Assessment of Immunogenicity to Emerging Variants of Concern: A randomized subset of 70 participants in Cohort 1 will be tested for additional SARS-CoV-2 variants of concern including Delta. No additional sample collection, procedures, or visits are required for this subset. A randomized subset of 82 participants in Cohort 2 comprised of younger adults (18 to 55 years of age) will provide samples for cellular immune response and mucosal antibody assessments and will also be tested for additional variants of concern including Delta.
--	--

Disclosure Statement:

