Supplemental Cohort 2, Main Arms: Adults vaccinated 4 to \leq 10 months prior will be stratified by primary vaccine and by age and randomized to receive 1 of the following as a single booster dose:

- Primed with Pfizer/BioNTech:
 - CoV2 preS dTM-AS03 (B.1.351):
 - 18-55 years of age: 515 participants
 - 56 years of age and older: 50 participants

- CoV2 preS dTM-AS03 (D614 + B.1.351):
 - 18-55 years of age: 515 participants
 - 56 years of age and older: 50 participants
- Primed with CoV2 preS dTM-AS03 (actual numbers will depend on eligibility and consent for Cohort 2 participation of participants enrolled in the Original Phase II Cohort; numbers below are estimates and subject to change):
 - CoV2 preS dTM-AS03 (D614):
 - 18-55 years of age: 270 participants
 - 56 years of age and older: 75 participants
 - CoV2 preS dTM-AS03 (B.1.351):
 - 18-55 years of age: 30 participants
 - 56 years of age and older: 75 participants
- Primed with Moderna:
 - CoV2 preS dTM-AS03 (B.1.351):
 - 18-55 years of age: 75 participants
 - 56 years of age and older: 25 participants
 - CoV2 preS dTM-AS03 (D614 + B.1.351):
 - 18-55 years of age: 75 participants
 - 56 years of age and older: 25 participants
- Primed with Oxford University/AstraZeneca:
 - CoV2 preS dTM-AS03 (B.1.351):
 - 18-55 years of age: 75 participants
 - 56 years of age and older: 25 participants
 - CoV2 preS dTM-AS03 (D614 + B.1.351):
 - 18-55 years of age: 75 participants
 - 56 years of age and older: 25 participants
- Primed with J&J/Janssen:
 - CoV2 preS dTM-AS03 (B.1.351):
 - 18-55 years of age: 75 participants
 - 56 years of age and older: 25 participants
 - CoV2 preS dTM-AS03 (D614 + B.1.351):
 - 18-55 years of age: 75 participants
 - 56 years of age and older: 25 participants

Supplemental Cohort 2 Exploratory B.1.351 Arms: Adults vaccinated 4 to \leq 10 months prior with the Pfizer/BioNTech mRNA vaccine will be stratified by age and randomized to receive a single booster dose of 1 of the following CoV2 preS dTM (B.1.351) formulations:

- 2.5 μ g antigen with full-dose AS03 adjuvant:
 - 18-55 years of age: 75 participants
 - 56 years of age and older: 25 participants
- 2.5 μ g antigen with half-dose AS03 adjuvant:

- 18-55 years of age: 75 participants
- 56 years of age and older: 25 participants
- 5 µg antigen with half-dose AS03 adjuvant:
 - 18-55 years of age: 75 participants
 - 56 years of age and older: 25 participants
- 5 µg antigen with no adjuvant:
 - 18-55 years of age: 75 participants

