---	--

vectored COVID-19 vaccine, the immune response to a booster dose of CoV2 preS dTM-AS03 (B.1.351) vaccine or CoV2 preS dTM-AS03 (D614 + B.1.351) vaccine compared to that observed immediately before booster.
 
8) To describe, in adults 18-55 years of age previously vaccinated with the Moderna vaccine, the immune response to a booster dose of CoV2 preS dTM-AS03 (B.1.351) vaccine or CoV2 preS dTM-AS03 (D614 + B.1.351) vaccine.
 
9) To describe, in adults 18-55 years of age previously vaccinated with the Oxford/AstraZeneca vaccine, the immune response to a booster dose of CoV2 preS dTM-AS03 (B.1.351) vaccine or CoV2 preS dTM-AS03 (D614 + B.1.351) vaccine.
 
10) To describe, in adults 18-55 years of age previously vaccinated with the J&J/Janssen vaccine, the immune response to a booster dose of CoV2 preS dTM-AS03 (B.1.351) vaccine or CoV2 preS dTM-AS03 (D614 + B.1.351) vaccine.
 
11) To describe, in adults 18-55 years previously vaccinated with any COVID-19 vaccine, the immune response a booster dose of CoV2 preS dTM-AS03 (B.1.351) vaccine or CoV2 preS dTM-AS03 (D614 + B.1.351) vaccine.
 
12) To compare the neutralizing antibody profile to the B.1.351 variant at D15 in each study Intervention Group and D36 in the Comparator Group, overall, by priming platform, and by priming vaccine.
 
13) To compare the neutralizing antibody profile against the D614G strain at D15 following a booster dose of CoV2 preS dTM-AS03 (D614 + B.1.351) vaccine and at D36 in the Comparator Group.
 
14) To describe, among adults previously primed with CoV2 preS dTM-AS03 (D614) vaccine, the immune response induced by a booster dose of CoV2 preS dTM-AS03 (D614) vaccine or CoV2 preS dTM-AS03 (B.1.351) vaccine or CoV2 preS dTM-AS03 (D614 + B.1.351) vaccine, overall, by priming dose, and by age.
 
15) To assess the neutralizing antibody profile to the D614G strain at D29, D91, D181, and D366 in each study Intervention Group, overall, by age group, by priming platform, and by priming vaccine.
 
16) To assess the neutralizing antibody to the B.1.351 variant at D29, D91, D181, and D366 in each study Intervention Group, overall, by age group, by priming platform, and by priming vaccine.
	
D01, against the D614G strain in each study Intervention Group
 
 • Individual serum neutralizing titer at D01 and D15 profile to the B.1.351 variant in each Intervention Group • Individual serum neutralization titer fold-rise post-vaccination relative to D01 at D15 profile to the B.1.351 variant in each Intervention Group • \geq 2-fold-rise and \geq 4-fold-rise in serum neutralization titer [post/pre] (fold-rise \geq 2 and \geq 4) at D15 relative to D01 profile to the B.1.351 variant in each study Intervention Group • Seroresponse rate, defined as a 4-fold or greater rise in serum neutralization titer [pre/post] at D15 relative to D01, profile to the B.1.351 variant in each study Intervention Group 
Endpoints for secondary objectives #15 and #16: neutralizing responses to be evaluated against the D614G strain and to the B.1.351 variant
 
 • Individual serum neutralizing titers in each Intervention Group at each pre-defined timepoint • Individual serum neutralization titer fold-rise post-vaccination at each pre-defined timepoint relative to D01 in each Intervention Group • \geq 2-fold-rise and \geq 4-fold-rise in serum neutralization titer [post/pre] (fold-rise \geq 2 and \geq 4) at each pre-defined timepoint relative to D01 in each study Intervention Group 
Endpoints for secondary objective #17:
 
 • Individual serum neutralizing titer at D01 and D15 against the D614G strain in each Intervention Group • Individual serum neutralization titer fold-rise post-vaccination relative to D01 at D15 against the D614G strain in each Intervention Group • \geq 2-fold-rise and \geq 4-fold-rise in serum neutralization titer [post/pre] (fold-rise \geq 2 and \geq 4) at D15 relative to D01 against the D614G strain in each study Intervention Group • Seroresponse rate, defined as a 4-fold-or greater rise in serum neutralization titer [pre/post] at D15 relative to D01, against the D614G strain in each study Intervention Group • Individual serum neutralizing titer at D01 and D15 profile to the B.1.351 variant in each Intervention Group • Individual serum neutralization titer fold-rise post-vaccination relative to D01 at D15 profile to the B.1.351 variant in each Intervention Group • \geq 2-fold-rise and \geq 4-fold-rise in serum neutralization titer [post/pre] (fold-rise \geq 2 and \geq 4) at D15 relative to D01 profile to the B.1.351 variant in each study Intervention Group • Seroresponse rate, defined as a 4-fold-or greater rise in serum neutralization titer [pre/post] at D15 relative to

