	
(Yes/No).
 
Eligible participants were randomly assigned to one of 3 study groups in a 1:1:1 ratio, corresponding to one of 3 formulations of CoV2 preS dTM-AS03 vaccine (with different antigen doses).
 
Supplemental Phase III Cohorts:
 
• Supplemental Cohort 1: previously-vaccinated participants will be stratified based on the priming vaccine received 4 to \leq 10 months prior and by age group (18-55 years of age and 56 years of age and older) and will receive a single booster dose of CoV2 preS dTM-AS03 (D614).• Supplemental Cohort 2, Main Arms: participants previously vaccinated with an mRNA or adenovirus-vectorized COVID-19 vaccine will be stratified based on the vaccine received 4 to \leq 10 months prior and by age group (18-55 years of age and 56 years of age and older) and randomly assigned to 1 of the following booster formulations in a 1:1 ratio:
○ CoV2 preS dTM-AS03 (B.1.351)○ CoV2 preS dTM-AS03 (D614 + B.1.351)Participants previously vaccinated 4 to \leq 10 months prior with the protein-based vaccine in the Original Phase II Cohort will be stratified by age group (18-55 years of age and 56 years of age and older) and randomly assigned to 1 of the following booster formulations in a 9:1 ratio (D614:B.1.351) for younger adults and a 1:1 ratio for older adults:
○ CoV2 preS dTM-AS03 (D614)○ CoV2 preS dTM-AS03 (B.1.351)• Supplemental Cohort 2 Exploratory B.1.351 Arms: participants previously vaccinated with the Pfizer/BioNTech mRNA vaccine will be enrolled after completion of enrollment of the above booster arms in Cohort 2 and will be stratified by age group (18-55 years of age and 56 years of age and older) and randomly assigned to receive 1 of the following CoV2 preS dTM (B.1.351) formulations in a 1:1:1:1 ratio:
○ 2.5 μg antigen with AS03 adjuvant○ 2.5 μg antigen with half-dose^a AS03 adjuvant
--	--

^a The half dose of AS03 and the full dose of AS03 contain amounts of tocopherol of 5.93 mg and 11.86 mg, respectively

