The reactogenicity and safety profile was similar across antigen dose groups and therefore the choice of antigen dose for the priming cohorts (naïve individuals), is consistent with the dose selected for the VAT00008 Phase III efficacy study and is largely informed by the observed immunogenicity profile in the naïve adults.

The neutralizing antibody responses to D614G were generally consistent without clear evidence of a dose effect across treatment groups in the overall naive population (18 years of age and older). A pattern of higher neutralizing antibody titers with higher antigen doses was observed in the younger adults age group, a pattern that was not evident in the older age group.

The ratio of neutralizing antibody responses in vaccinees compared to human convalescent sera has been modeled to correlate with observed vaccine efficacy against the homologous variants. In these models, ratios of 1 correlate to vaccine efficacy of ~80-90% and ratios of 0.8 correlate to vaccine efficacy of ~70-80% (62) (63). This relationship is modeled for neutralizing antibody responses and efficacy against the homologous variants, with the expectation that the predicted vaccine efficacy against heterologous variants will be lower for a similar ratio of vaccine-induced antibody response to human convalescent sera (HCS).

In the Original Phase II Cohort in this protocol the geometric mean titers (GMTs) observed in naïve individuals at D36 in the overall study population were comparable to GMTs observed in a panel of human convalescent sera (GMT 2140; 95% confidence interval [CI]: 1543, 2967; N = 79) measured in the same pseudovirus neutralizing assay, laboratory, and time frame. In younger adults, the ratio of neutralizing antibody titers to HCS was > 1 (ie, 1.37, 1.85, and 2.25, respectively) in the younger naïve adults; and in the older naïve adults, the ratio ranged from 0.7 - 0.75 across the 3 dosages. Based on these pseudovirus neutralizing ratios (vaccine induced/HCS) there is expected to be little difference in vaccine protection between antigen dose levels.

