Eligible participants transitioning from the VAT00002 Original Phase II Cohort who have received the CoV2 preS dTM-AS03 (D614) candidate vaccine (targeted N = 450; actual number to be determined by number of VAT00002 participants meeting eligibility criteria for transition) will be randomized to receive a single injection of either the CoV2 preS dTM-AS03 (D614) or the CoV2 preS dTM-AS03 (B.1.351) booster vaccine. Randomization will occur by age strata (assumption that about 2/3 of participants will be 18-55 years of age (ie, 300 adults 18-55 years old, allocation ratio of 9:1 between CoV2 preS dTM-AS03 [D614] group and the CoV2 preS dTM-AS03 [B.1.351] group); the actual number and age distribution will be determined by characteristics of those who meet eligibility criteria for transition). A subset of 10% of participants aged 18-55 (~30 participants in the 2 Booster Groups combined) will be randomly assigned to collect CMI and mucosal samples plus variant testing.

Site staff will connect to the IRT system, enter the identification and security information, and confirm a minimal amount of data in response to IRT prompts. The IRT will collect information on age-group, priming vaccine, high-risk medical conditions, and ethnicity/race (the last 2 for monitoring purposes and high-risk medical conditions for potential capping). The IRT will then provide the group assignment (intervention arm and CMI/mucosal subset [if applicable]). The full detailed procedures for group allocation are described in the Operating Guidelines.

Supplemental Cohorts Comparator Group:

This Group will be open-label and not randomly assigned as all eligible participants will have common baseline characteristics (previously unvaccinated) and all will receive two injections of the CoV2 preS dTM-AS03 (D614) candidate vaccine 21 days apart. Eligible participants must be 18-55 years of age and have a negative baseline SARS-CoV-2 rapid serodiagnostic test to be enrolled into this group. A subset of 5% of participants aged 18-55 (~26 participants) will be randomly assigned to variant testing subsets.

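### Protein-primed participants are allocated 9:1 (D614:B.1.351) if younger and 1:1 if older, so the unadjusted all-age and by-priming-dose contrasts of the two boosters mix vaccine with age

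*Protocol*

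**What the plan says.** Protocol Section 4.1 (Table 4.1) allocates the protein-primed participants "in a 9:1 ratio (D614:B.1.351) for younger adults and a 1:1 ratio for older adults"; the Synopsis says the same. Section 6.3.1 plans "300 adults 18-55 years old, allocation ratio of 9:1 between CoV2 preS dTM-AS03 [D614] group and the CoV2 preS dTM-AS03 [B.1.351] group", that is 270 and 30. In the older stratum the Synopsis gives each arm "56 years of age and older: 75 participants". It adds that the "numbers below are estimates and subject to change", because they depend on who transitions from the Original Phase II Cohort.

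Cohort 2 secondary objective 14 (Table 3.1) describes the booster response in this group "overall, by priming dose, and by age". Its endpoints are titers, fold-rises and seroresponse rates.

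For secondary immunogenicity, Section 9.4.2.2.3 states that "GMT ratios between injection groups will be summarized along with their 95% CIs using the normal approximation of log-transformed titers". Differences in the percentages of responders and of participants with 2- and 4-fold rises use the Newcombe-Wilson score method. The interval method of Section 9.4.2.2.1 (Welch's t-interval for between-group GMT ratios) also applies. None of these is stratified by age or has an age term. The same section plans subgroup analyses by age group.

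**The concern.** In this group age decides the chance of receiving each booster. The protocol itself reports higher titers in younger adults after the primary series. An all-age comparison of the arms that takes no account of the stratum therefore confounds vaccine with age. The same holds within each priming dose, because the allocation ratio depends on age alone.

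This is the trial's only randomized comparison of the D614 booster with the monovalent B.1.351 booster. The other main-arm participants in Cohort 2 are randomized between B.1.351 and the bivalent vaccine, and Cohort 1 is open-label and not randomized. The by-age cells are also thin, with 30 younger B.1.351 recipients planned in total, so readers are likely to turn to the pooled figures. If younger people respond better, those figures flatter D614.

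**Working it through.** **The plan's own figure.** The protocol states no figure for this contrast. The nearest is the protein-primed D614 row of Table 9.1, which concerns ages 18-55 only. Its inputs are evaluable n of 270 × 0.97 and 515 × 0.90, log10 SDs of 1.0 and 0.65, a difference of log10(1.5) − log10(1/1.5) = 0.352, and one-sided alpha 0.025/3. They give non-inferiority power of 99.7% and superiority power above 99.9%. Both reproduce, and neither depends on the age mix.

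**Age mix by arm.**
- D614: 270/(270 + 75) = 270/345 = 78.3% younger.
- B.1.351: 30/(30 + 75) = 30/105 = 28.6% younger.
- Gap: 0.783 − 0.286 = 0.497.

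**Formula.** An arm's mean log titer is p·μ(younger) + (1 − p)·μ(older), where p is its younger share. If the two boosters are identical, the crude D614/B.1.351 GMT ratio is R^0.497, where R is the younger/older GMT ratio.

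**Values of R.** Section 4.3 gives D36 titers relative to convalescent sera in naïve participants. At 18-59 years they are 1.37, 1.85 and 2.25 for 5, 10 and 15 µg. For the others, "in the older naïve adults, the ratio ranged from 0.7 - 0.75 across the 3 dosages".

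| Source of R | R | Crude ratio, identical boosters |
|---|---|---|
| 5 µg (1.37/0.75 to 1.37/0.70) | 1.83-1.96 | 1.35-1.40 |
| 10 µg (1.85/0.75 to 1.85/0.70) | 2.47-2.64 | 1.57-1.62 |
| 15 µg (2.25/0.75 to 2.25/0.70) | 3.00-3.21 | 1.73-1.79 |
| Geometric mean over doses | 2.38-2.55 | 1.54-1.59 |
| Assumed | 2.0 | 1.41 |
| Assumed | 1.5 | 1.22 |
| Assumed | 1.25 | 1.12 |
| No age effect | 1.0 | 1.00 |

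**Effect on the interval.** With SD 1.0 (log10), the crude standard error is √(1/345 + 1/105) = 0.111. With no vaccine difference, the crude 95% CI would exclude 1 in about 22% of trials at a distortion of 1.35, 45% at 1.6 and 62% at 1.79.

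**Sensitivity to the arm sizes.** Let f be the younger share among those who transition. The arm shares are 0.9f/(0.9f + 0.5(1 − f)) and 0.1f/(0.1f + 0.5(1 − f)). For f from 0.3 to 0.8 the gap stays between about 0.36 and 0.50, so the confounding does not hinge on the exact counts.

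**Cost of stratifying.** The stratified information is 270 × 30/300 + 75 × 75/150 = 27 + 37.5 = 64.5, so the standard error is 1/√64.5 = 0.125.
- Overall, the 95% CI factor is 10^(1.96 × 0.125) ≈ 1.75, against 10^(1.96 × 0.111) ≈ 1.65 for the crude ratio.
- Within a priming dose (one third of the numbers, assuming an even split), it is about 2.65 against 2.39.

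**The case against.** The strongest reply is that objective 14 is worded as a description of each booster, whereas objectives 12 and 13 are worded as comparisons, and with the Comparator Group. An all-age D614 versus B.1.351 ratio in protein-primed participants is named nowhere, and the sentence in Section 9.4.2.2.3 is generic. Section 9.4.1 makes secondary objectives without a hypothesis test descriptive. Results by age are required by the objective itself. Section 9.4 defers technical detail to the SAP.

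Much of this stands. The point applies only where the two arms are contrasted with the ages pooled. A GMT describing one arm is not biased by its age mix. The by-age results are free of the problem, so it would be wrong to say that the plan ignores age. The tested protein-primed hypotheses are limited to 18-55 years and compare D614 with the Comparator Group or with pre-booster titers.

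What does not stand is that this is only missing detail. The protocol sets unequal allocation by age, asks for results overall and by priming dose, and states between-group methods without the stratum. Followed as written, those methods give confounded contrasts with 95% CIs attached.

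A reader might also infer that age alone makes D614 look about 1.6-fold better. The documents do not establish that. A distortion of 1.6 needs R of about 2.6, taken from naïve adults after two priming doses with an age cut at 60. The affected people are already primed, receive one booster and are cut at 56, and the protocol gives no booster age effect for them. Nor is the trial's 1.5-fold margin a fair yardstick, since it belongs to other comparisons.

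**Conclusion.** The concern holds in a limited form. Pooled-age and by-priming-dose contrasts of the D614 and B.1.351 boosters in protein-primed participants, computed as Section 9.4.2.2.3 states, are confounded by age because of the allocation. The distortion in the GMT ratio is about 1.35 to 1.8 in favour of D614 if the primary-series age gap persists after boosting. It falls to about 1.22 at an age ratio of 1.5 and vanishes if there is no age effect. These figures rest on the planned arm sizes, which are estimates. For fold-rise and seroresponse the protocol gives no age effect after boosting, so even the direction is unknown. No hypothesis test is affected and the results concerned are descriptive, so the severity is moderate rather than must-fix.

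**What to change.** Add one sentence to Section 9.4.2.2.3 and carry it into the SAP. It should say that every pooled-age protein-primed contrast between the D614 and B.1.351 boosters, overall or by priming dose, is stratified by or adjusted for the randomization age stratum. For GMT ratios this could be log10 titer on arm and age stratum, or stratum-specific results combined with common weights. Fold-rise and seroresponse contrasts should use the same common weights. Contrasts not handled this way should be shown only within age group.

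This removes the distortion due to the unequal age-stratum mix and needs no extra data or participants. The price is the slightly wider interval shown in the working.
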